Appendix 8 Liver Safety: Suggested Actions and Follow-up Assessments

Not applicable.

Appendix 9 **Medical Device Incidents: Definition and Procedures for Recording, Evaluating, Follow-up, and Reporting**

Definitions of a Medical Device Incident

The detection and documentation procedures described in this protocol apply to all Sponsor medical devices provided for use in the study (see Section 6.1) for the list of Sponsor medical devices).

Medical Device Incident definition

- A Medical Device Incident is any malfunction or deterioration in the characteristics and/or performance of a device as well as any inadequacy in the labeling or the instructions for use which, directly or indirectly, might lead to or might have led to the death of a subject/user/other person or to a serious deterioration in his/her state of health.
- Not all incidents lead to death or serious deterioration in health. The nonoccurrence of such a result might have been due to other fortunate circumstances or to the intervention of health care personnel.

It is sufficient that:

- An **incident** associated with a device happened.

AND

- The **incident** was such that, if it occurred again, might lead to death or a serious deterioration in health.

A serious deterioration in state of health can include any of the following:

- Life-threatening illness.
- Permanent impairment of body function or permanent damage to body structure.
- Condition necessitating medical or surgical intervention to prevent 1 of the above.
- Fetal distress, fetal death, or any congenital abnormality or birth defects.

Examples of incidents

- A subject, user, caregiver, or healthcare professional is injured as a result of a medical device failure or its misuse.
- A subject's study treatment is interrupted or compromised by a medical device failure.
- A misdiagnosis due to medical device failure leads to inappropriate treatment.
- A subject's health deteriorates due to medical device failure.

Documenting Medical Device Incidents

Medical Device Incident documenting

- Any Medical Device Incident occurring during the study will be documented in the subject's medical records, in accordance with the Investigator's normal clinical practice, and on the appropriate form of the CRF.
- For incidents fulfilling the definition of an AE or an SAE, the appropriate AE/SAE CRF page will be completed as described in [Appendix 4](#).
- The CRF will be completed as thoroughly as possible and signed by the Investigator before transmittal to the Sponsor or designee.
- It is very important that the Investigator provides his/her assessment of causality (relationship to the medical device provided by the Sponsor) at the time of the initial AE or SAE report and describes any corrective or remedial actions taken to prevent recurrence of the incident.

A remedial action is any action other than routine maintenance or servicing of a medical device where such action is necessary to prevent recurrence of an incident. This includes any amendment to the device design to prevent recurrence.

Appendix 10 Audiology Testing Template

EAR, NOSE AND THROAT CARE FOR CHILDREN AND ADULTS

Name _____ Date _____

Date of Birth _____

PURE TONE AUDIOMETRY

		RIGHT EAR						LEFT EAR											
		FREQUENCY (Hz)						FREQUENCY (Hz)											
		125	250	500	1000	2000	4000	8000	125	250	500	1000	2000	4000	8000				
HEARING LEVEL in dB (re: ANSI® 1969)		0	10	20	30	40	50	60	70	80	90	100	110	100	110				
reliability:		 good  fair  poor						 good  fair  poor											

RIGHT EAR

SPEECH RECEPTION THRESHOLD	WORD RECOGNITION	WORD RECOGNITION	UCL
MASK _____	MASK _____	MASK _____	dB HL
PRES. LEVEL _____	_____ %	_____ %	

LEFT EAR

SPEECH RECEPTION THRESHOLD	WORD RECOGNITION	WORD RECOGNITION	UCL
MASK _____	MASK _____	MASK _____	dB HL
PRES. LEVEL _____	_____ %	_____ %	

EFFECTIVE MASKING USED WHEN APPROPRIATE ALL RESULTS RE: 1996 ANSI NORMS

Compliance (cm³)

Pressure (da Pa)

Jerger Type _____ ecV _____

Audiological Findings and Recommendations

Screening Reflex Threshold

Probe Right

	IPSI	CONTRA
500		
1000		
2000		
4000		

Probe Left

	IPSI	CONTRA
500		
1000		
2000		
4000		

Compliance (cm³)

Pressure (da Pa)

Jerger Type _____ ecV _____

AUD-1 (07/2017)

Appendix 11 Protocol Amendment History

The Protocol Amendment Summary of Changes Table for the current amendment is located directly before the Table of Contents (TOC).

1. INTRODUCTION

This document describes the rules and conventions to be used in the presentation and analysis of safety and pharmacokinetic (PK) data for Protocol OP0201-C-002. It describes the data to be summarized and analyzed, including specifics of the statistical analyses to be performed.

This statistical analysis plan (SAP) is based on the protocol Amendment 1 dated 09OCT2018.

2. STUDY OBJECTIVES

2.1. PRIMARY OBJECTIVE

- To evaluate the safety and tolerability of OP0201 30 mg per day (given as 2 sprays per nostril 3 times a day [TID] for 14 consecutive days) and OP0201 60 mg per day (given as 4 sprays per nostril TID for 14 consecutive days) compared to 0 mg placebo (HFA-134a only) administered in a similar parallel-group fashion TID for 14 consecutive days in healthy adult volunteers.

2.2. SECONDARY OBJECTIVES

- To evaluate if any systemic exposure of dipalmitoylphosphatidylcholine (DPPC) can be detected in serum at levels higher than endogenous DPPC levels in serum in up to 15 healthy adult volunteers who will be evaluated in the Cohort B dose (OP0210 60 mg per day) versus placebo.
- To evaluate if any systemic exposure of cholestryl palmitate (CP) can be detected in serum at levels higher than endogenous CP levels in serum in up to 15 healthy adult volunteers who will be evaluated in the Cohort B dose (OP0210 60 mg per day) versus placebo (if feasible).

3. STUDY ENDPOINTS

3.1. PRIMARY ENDPOINTS

- Adverse events (AEs), otoscopy, tympanometry, nasal and epipharynx endoscopy, University of Pennsylvania Smell Inventory Test (UPSIT) olfactory test, audiology pure tone hearing test, triplicate 12-lead electrocardiogram (ECG), physical examination, vital signs, and clinical laboratory tests.

Document: Statistical Analysis Plan

Author: [REDACTED]

Version Number:

2.0

Version Date:

03APR2019

[REDACTED]

[REDACTED]

3.2. SECONDARY ENDPOINTS

- Maximum baseline adjusted serum concentration (C_{max}) of DPPC on Day 14.
- Time to maximum concentration (t_{max}) of DPPC on Day 14.
- Maximum baseline adjusted serum concentration (C_{max}) of CP on Day 14 (if feasible).
- Time to maximum concentration (t_{max}) of CP on Day 14 (if feasible).
- Additional parameters may be calculated, if appropriate.

4. STUDY DESIGN

4.1. GENERAL DESCRIPTION

This is a randomized, double-blind, placebo-controlled, parallel-group, dose-escalation study in healthy volunteers to evaluate the safety and tolerability of OP0201 administered intranasally 3 times a day (TID) using a metered dose inhaler (MDI) compared to a matching placebo (HFA-134a minus active ingredients) administered intranasally TID using a MDI for 14 consecutive days (see Figure 1 for the study schematic). The plan is to enroll up to 30 subjects at 1 study center in the US. Two dose cohorts are planned (Cohort A and Cohort B; N=15 per cohort, see Cohort Dosing below, Table 1). Within each cohort, subjects will be randomized in a 4:1 ratio to receive either OP0201 or placebo. After all subjects in Cohort A have completed the Day 14 visit, a Safety Review Committee (SRC) will review all the blinded safety data to determine whether the doses administered are safe and well tolerated. The SRC will make a recommendation to escalate to the next cohort (Cohort B) or not.

Document:	Statistical Analysis Plan	Version Number:	2.0
Author:	[REDACTED]	Version Date:	03APR2019

[REDACTED]

[figure not shown]
[REDACTED]

Table 1 Dose Cohorts and Dose Regimen

Cohort	Dose Regimen	Cohort Dose Allocation		Total Subjects in Each Cohort	Total Subjects Per Dose Group
		Per Day Total Dose (mg)	Cumulative Total Dose (mg)		
A	2 sprays per nostril TID x 14 days	OP0201 (30 mg) ^a Placebo (0 mg)	OP0201 (420 mg) ^a Placebo (0 mg)	15	N=12 (OP0201) N=3 (Placebo)
B	4 sprays per nostril TID x 14 days	OP0201 (60 mg) ^a Placebo (0 mg)	OP0201 (840 mg) ^a Placebo (0 mg)	15	N=12 (OP0201) N=3 (Placebo)

a 2.5 mg per spray

N = number of subjects; TID = three times a day

Figure 1 Study Schema

Document: Statistical Analysis Plan

Author: [REDACTED]

Version Number:

Version Date:

2.0

03APR2019

[figure not shown]
4.2. SCHEDULE OF EVENTS

Table 2 Schedule of Activities

Study Period (with Visit Windows)	Screening Period	Confinement Period ^a (In-Clinic)						Study Exit	
		Day -1 (Admission)	Day 1 (Enrollment)	Day 4	Day 8	Day 14	Day 15		
Informed Consent/Authorization	X								
Demographics	X								
Inclusion/Exclusion	X	X							
Pregnancy Test (Urine) ^c	X	X						X	X
Follicle Stimulating Hormone Test ^d	X								
Urine Drug Screen ^e	X	X							
Viral Serology ^f	X								
Medical, Surgical, Ear History	X								
Physical Examination ^g	X							X	X
Vital Signs ^h	X	X	X	X	X	X	X	X	X
12-Lead ECG ⁱ	X		X			X		X	X
Ear History	X								
Otoscopy ^j	X	X		X	X	X			
Tympanometry	X	X		X	X	X		X ^o	X ^p

Document: Statistical Analysis Plan

Author:

Version Number:

2.0

Version Date:

03APR2019

Study Period (with Visit Windows)	Screening Period	Confinement Period ^a (In-Clinic)						Study Exit		
		Days -28 to -1 (Screening) In-Clinic	Day -1 (Admission)	Day 1 (Enrollment)	Day 4	Day 8	Day 14	Day 15	Day 21 (+5 Day) In-Clinic	EaT ^b
Nasal and Epipharynx Endoscopy ^k	X	X			X	X				
Clinical Laboratory Tests ^l	X					X				X
UPSIT Olfactory Test ^m	X				X	X			X ⁿ	X
Audiology Pure Tone Hearing Test	X					X			X ^o	X ^p
Admission		X								
Train Participant on Study Product Administration ^q		X	X							
Randomization		X								
Study Treatment ^r			X	X	X	X				
Concomitant Medications	X	X	X	X	X	X	X		X	X
Adverse Events	X	X	X	X	X	X	X		X	X
PK Sample Collection			X ^r			X ^s				
Device Experience Questionnaire – Subject ^t							X			X ^u
Device Experience Questionnaire – Study Center Staff Administering the Treatment ^t							X			X ^u

EaT = Early termination; ECG = Electrocardiogram; IP = Investigational Product; PK = pharmacokinetic; UPSIT = University of Pennsylvania Smell Inventory Test.

Document: Statistical Analysis Plan

Author: [REDACTED]

Version Number:

2.0

Version Date:

03APR2019

- a Eligible healthy volunteers will be admitted to the study center on Day -1 and be randomized on Day -1. Subjects will remain resident at the study center until after all the Day 15 assessments have been completed.
- b EaT: To be performed if the subject was treated but early discontinue from the study.
- c For all females, urine pregnancy test must be negative to meet study enrollment criteria.
- d To be performed on postmenopausal women at Screening to confirm menopausal status (see Protocol Appendix 6).
- e Specific tests to be conducted are listed in Protocol Table 8, Appendix 3.
- f To be performed at Screening only (see Protocol Table 8, Appendix 3).
- g Includes general appearance, overall status of the skin, head, neck, trunk, eyes, heart and lungs (eg, breathing sounds), abdomen, extremities, lymph nodes. Height and weight are recorded only at the Screening visit.
- h Vital signs include blood pressure, respiratory rate, pulse rate, and body temperature.
- i A single 12-lead ECG will be collected for screening purposes. For subjects in Cohort A, a single 12-lead ECG will be collected on Day 1 prior to the first dose and on the study exit visit (Day 21). For subjects in Cohort B, triplicate ECGs will be collected on Day 1: 30 and 60 minutes prior to the first dose, Day 14: 30 minutes prior to the last dose and 5, 20, 35, 50 minutes following the last dose on Day 14. In cases where ECG and PK sampling overlap, ECGs should be collected first, to ensure that PK samples are collected at the scheduled time point.
- j Otoscopy involves ear endoscopy, taking a picture of the tympanic membrane and assessing if there are any abnormal findings.
- k Nasal endoscopy will include a measurement of nasal cavity length (in mm) at the Screening visit only. For all other scheduled assessments, the nasal and epipharynx endoscopy assessment should be done prior to the first dose of the day.
- l Includes hematology, clinical chemistry, coagulation and urinalysis (see Protocol Table 8, Appendix 3).
- m At Screening, a total UPSIT score of ≥ 35 (for females) and a total UPSIT score of ≥ 34 (for males) is required to meet study enrollment criteria.
- n To be collected at the Day 21 study exit visit only if abnormal at the Day 14 visit. Abnormal is defined as UPSIT score < 35 (for females) and < 34 (for males) (see Protocol Section 8.2.8).
- o Audiology pure tone hearing test if abnormal in either ear at Day 14 visit. Abnormal defined as > 20 dB worsening from baseline at Day 14 visit (See Protocol reference Rosenfeld et al, 2004). Tympanometry is performed along with the Audiology pure tone hearing test so if the subject requires a hearing test at this visit, tympanometry will also be performed.
- p Audiology pure tone hearing test and tympanometry not required if subjects drops out before Day 14, but if they drop out after Day 14 and had an abnormal test result at Day 14 visit, then every effort should be made to have the patient complete these assessments at the EaT visit.
- q Study subjects need to be trained on study treatment administration on Day -1 or on Day 1, prior to the first dose.
- r Study treatment dosing recommendation: the first dose at 9:00 am, second dose at 16:00 pm and the third dose at 23:00 pm.

- s PK sample timing Cohort B only: Day 1: 30 and 60 minutes prior to the first dose, Day 14: 30 minutes prior to the last dose and 5, 20, 35, 50 minutes following the last dose on Day 14. The 5-minute PK sample should be collected within ± 2 minutes of the scheduled time and the 20-minute PK sample should be collected within $+5$ minutes of the scheduled time. All other PK samples should be collected within ± 5 minutes of the scheduled time.
- t To be completed before discharge from the study center on the morning of Day 15 (See Protocol Appendix 7 for an example).
- u This assessment is needed only if subjects discontinue the study prior to completing the questionnaire on Day 15.

Document: Statistical Analysis Plan
Author: [REDACTED]

Version Number: 2.0
Version Date: 03APR2019

[REDACTED]
[REDACTED]

4.3. CHANGES TO ANALYSIS FROM PROTOCOL

Pharmacokinetic analysis of CP will not be completed because the quantitative method for the determination of CP is not feasible. This resulted in the below changes from the protocol to the SAP:

Protocol	SAP
Secondary Objective : To evaluate if any systemic exposure of cholesteryl palmitate (CP) can be detected in serum at levels higher than endogenous CP levels in serum in up to 15 healthy adult volunteers who will be evaluated in the Cohort B dose (OP0210 60 mg per day) versus placebo.	To evaluate if any systemic exposure of cholesteryl palmitate (CP) can be detected in serum at levels higher than endogenous CP levels in serum in up to 15 healthy adult volunteers who will be evaluated in the Cohort B dose (OP0210 60 mg per day) versus placebo (if feasible).

Secondary Endpoint: Maximum baseline adjusted serum concentration (C_{max}) of CP on Day 14.	
Maximum baseline adjusted serum concentration (C_{max}) of CP on Day 14 (if feasible).
Secondary Endpoint : Time to maximum concentration (t_{max}) of CP on Day 14.	Time to maximum concentration (t_{max}) of CP on Day 14 (if feasible).

5. PLANNED ANALYSES

5.1. SAFETY REVIEW COMMITTEE (SRC)

After all subjects in Cohort A have completed the Day 14 visit, a SRC will review all the blinded safety data to determine whether the doses administered are safe and well tolerated. The SRC will make a recommendation to escalate to the next cohort (Cohort B) or not.

■ Data Management will entirely support the provision of blinded data for the SRC meeting including creating the SRC plan and will deliver required material directly to the SRC committee for this purpose.

■ Biostatistics will not be involved in this blinded review.

5.2. INTERIM ANALYSIS

There are no formal interim analyses planned for this study.

Document:	Statistical Analysis Plan	Version Number:	2.0
Author:	■■■■■	Version Date:	03APR2019
■■■■■	■■■■■	■■■■■	■■■■■
■■■■■	■■■■■	■■■■■	■■■■■

5.3. FINAL ANALYSIS

All final, planned analyses identified in this SAP will be performed by [REDACTED] Biostatistics following sponsor authorization of this SAP, identification of major protocol deviations requiring analysis exclusions, database lock, determination of analysis sets, and unblinding of treatment.

6. ANALYSIS SETS

6.1. ENTERED ANALYSIS SET

The entered analysis set will contain all screened subjects who provide informed consent for this study, including screen failure subjects. Subjects in this population will be used for pre-treatment adverse events listing including serious adverse events (SAE), disposition listing and summary. Demographics and eligibility criteria will be presented separately for screen failure subjects.

6.2. SAFETY ANALYSIS SET

The safety analysis set will contain all subjects who are assigned to study treatment and receive at least one dose of any study medication (OP0201 or Placebo) and will be analyzed according to treatment received. Subjects in this population will be used for all safety, dosing, and demographic summaries.

6.3. PHARMACOKINETIC ANALYSIS SET

The pharmacokinetic analysis set will include all subjects in Cohort B who receive at least 1 dose of study drug, OP0201 or placebo, and have at least 1 quantifiable serum DPPC concentration collected post-dose without any important protocol deviations/violations or events thought to significantly affect the PK of DPPC. Subjects in this population will be used for all PK analyses and summaries.

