9.3 Populations for Analyses

For purposes of analysis, the analysis sets in [Table 7](#) are defined.

Table 7 Analysis Sets

Analysis Set	Description
Entered Analysis Set	All subjects who sign the informed consent form.
Safety Analysis Set	All subjects who receive any study treatment (OP0201 or placebo). Subjects will be analyzed according to the treatment they received.
Pharmacokinetic Analysis Set	All subjects in Cohort B who received at least 1 dose of OP0201 and have 1 quantifiable serum DPPC or CP concentration collected post-dose without important protocol deviations/violations or events thought to significantly affect the pharmacokinetics.

CP = cholestryol palmitate; DPPC = dipalmitoylphosphatidylcholine

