9.4.2 Pharmacokinetic Analyses

Pharmacokinetic analyses will be described in the SAP that will be finalized before database lock. All PK analyses will be performed on the PK Analysis Set.

Observed and baseline adjusted serum DPPC concentrations will be summarized by time point. Observed and baseline adjusted serum CP concentrations (if available) will be summarized by time point.

Serum DPPC PK parameters (if any) will be summarized. Serum CP PK parameters (if available) will be summarized.

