7.1. SUMMARY STATISTICS

For qualitative or categorical variables, the population size (N for sample size and n for number of non-missing values) and the percentage (of available data) for each class of the variable will be presented. Quantitative variables, including PK variables (serum concentrations and PK parameters for DPPC) will be summarized using descriptive statistics, including N, n, mean, standard deviation (SD), coefficient of variation (CV%) as appropriate, median, minimum, and maximum values. Geometric mean (GMean) and geometric coefficient of variation (GCV%) will be included for PK parameters, where applicable. For t_{max} , only N, n, median, minimum, and maximum will be reported. Coefficient of variation will not be presented for change-from–baseline results. A minimum of 3 valid data values (n=3) is required for all descriptive statistics to be generated. If n is less than 3, only N, n, minimum, and maximum will be reported.

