16. PHARMACOKINETIC ANALYSIS

16.1. SERUM CONCENTRATION DATA

Subjects with partial data will be evaluated on a case-by-case basis to determine if sufficient data are available for reliable estimation of PK parameters. If a subject is missing both predose sample collections, their observed concentrations will be listed and summarized but not included in baseline-corrected listings or summaries.

A listing of PK blood sample collection times as well as derived sampling time deviations will be provided. Baseline-corrected DPPC serum levels will be derived by subtracting the observed levels at sample time on Day 14 from the mean baseline on Day 1 predose, if possible. If the resulting value is negative, the estimated baseline-corrected level will be set to zero (0) for purposes of reporting and subsequent analysis.

Observed and baseline-corrected serum concentrations will be summarized by treatment using

Document: Statistical Analysis Plan
Author: [REDACTED]

Version Number:
Version Date:

2.0
03APR2019

descriptive statistics. Predose and postdose concentrations of DPPC that are below the limit of quantification (BLQ) will be treated as zero for the computation of descriptive statistics.

A subject listing of all observed and baseline-corrected concentration-time data will be presented by treatment. Figures of arithmetic mean of observed and baseline-corrected concentration-time data (\pm SD, as appropriate) will be presented by treatment on linear and semi-logarithmic scales. Individual subject observed concentration-time data will be graphically presented on linear and semi-logarithmic scales.

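### The PK set requires a quantifiable post-dose DPPC value, so a dosed subject whose post-dose samples are all BLQ is dropped instead of counted as zero

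*SAP*

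**What the plan says.** The secondary objective in SAP 2.2 asks whether systemic DPPC "can be detected in serum at levels higher than endogenous DPPC levels in serum" in Cohort B. The endpoint in SAP 3.2 is baseline-adjusted Cmax on Day 14, with tmax.

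Entry to the PK set depends on a measured result. SAP 6.3 requires that subjects "have at least 1 quantifiable serum DPPC concentration collected post-dose", and adds: "Subjects in this population will be used for all PK analyses and summaries". Protocol 9.3 (Table 7) asks that subjects "received at least 1 dose of OP0201 and have 1 quantifiable serum DPPC or CP concentration collected post-dose", and Protocol 9.4.2 states: "All PK analyses will be performed on the PK Analysis Set". SAP 4.3 says the CP assay is not feasible, so in practice both filters rest on DPPC.

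Other sections say how low values are handled. In SAP 16.1, predose and postdose values "below the limit of quantification (BLQ) will be treated as zero" in descriptive statistics, and a negative baseline-corrected level is set to zero and kept. SAP 16.2 sets BLQ values to zero in most positions of the profile when PK parameters are calculated.

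On placebo, SAP 6.3 includes placebo recipients, Protocol Table 7 names OP0201 recipients only, and Protocol 8.5.2 says that post-dose samples from placebo subjects will not be assayed.

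**The concern.** The entry condition is applied to the same post-dose measurements that the PK analysis summarises. A dosed subject with every post-dose sample BLQ gives valid information, and it points towards no measurable exposure. Under SAP 6.3 that subject leaves all PK summaries, so the zero that SAP 16.1 would assign is never used. A subject with quantifiable endogenous DPPC and no rise stays in and contributes zero to the baseline-corrected summaries. Both subjects show no increase, but only one is counted.

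At stake is the level of the post-dose means and of mean baseline-corrected Cmax in an arm of 12. The plan also cannot show what share of dosed subjects had a quantifiable value, because within the PK set that share is 100% by construction.

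**Working it through.** **Inputs.** Cohort B has 15 subjects allocated 4:1 (SAP 4.1, Table 1): 15 x 4/5 = 12 OP0201 and 3 placebo, as stated. On Day 14 there are four samples after the last dose (5, 20, 35 and 50 minutes) and one 30 minutes before it. The plan gives no power, SD, assay limit (LLOQ) or serum DPPC level, so there is no figure of its own to reproduce on this point.

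**Step 1: the two null cases, side by side.** Baseline correction is taken as observed minus baseline. SAP 16.1 words the subtraction the other way round, which is a separate matter.
- Quantifiable, no rise (illustration: baseline 100, Day 14 values 97 to 100): meets SAP 6.3; corrected values 0; kept, with Cmax 0.
- All post-dose samples BLQ: observed values 0 under SAP 16.1; corrected values 0 minus baseline, at most 0, so set to 0; Cmax would be 0. Fails SAP 6.3; dropped.

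The parameter rules in SAP 16.2 are worded around quantifiable neighbouring values, so they do not literally describe an all-BLQ profile; zero is the natural extension.

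**Step 2: size if k OP0201 subjects are all-BLQ.** The dropped subjects would each add 0 to the sum, so the sum S is unchanged and only the divisor moves. The ratio of the PK-set mean to the all-dosed mean is [S/(12-k)] / [S/12] = 12/(12-k).

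| k | PK set n | true share with a quantifiable value | factor on the mean |
|---|---|---|---|
| 0 | 12 | 100% | 1.00 |
| 1 | 11 | 91.7% | 1.09 |
| 3 | 9 | 75.0% | 1.33 |
| 6 | 6 | 50.0% | 2.00 |

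The factor applies to observed post-dose means at each time and to mean baseline-corrected Cmax.

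**Step 3: how likely is k of 1 or more?** This is by assumption only.
- If BLQ status is independent between samples with probability 0.10, a subject is all-BLQ over four samples with probability 0.10^4 = 0.0001, and the chance that any of 12 is dropped is 1 - (1 - 0.0001)^12 = 0.0012. At 0.50 per sample it is 1 - (1 - 0.0625)^12 = 0.54.
- If BLQ status is a fixed property of the subject, with 1%, 10% or 25% of subjects all-BLQ, the chance is 1 - 0.99^12 = 0.11, 1 - 0.90^12 = 0.72 and 1 - 0.75^12 = 0.97.

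**Step 4: size against the assay limit.** Lognormal simulation with assumed between-subject CV 40%, within-subject CV 15%, four post-dose samples and no exposure:

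| median level / LLOQ | subjects dropped | mean overstated by |
|---|---|---|
| 1 | 35% | 54% |
| 1.5 | 8% | 9% |
| 2 | 1.7% | 1.7% |
| 2.5 | 0.4% | 0.4% |
| 3 | 0.1% | 0.1% |
| 5 | none | none |

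As a check, the overstatement should be about 1/(1 - share dropped) - 1: 1/0.65 - 1 = 54%, and 1/0.92 - 1 = 9%.

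**The case against.** The best answer is that DPPC is endogenous. The plan treats its serum level as something to be established by assay, and it kept DPPC while giving up CP as not feasible. If every subject's endogenous level is comfortably quantifiable, the rule removes nobody. That stands as a possibility, and Step 4 shows that about twice the limit is enough under the assumptions used. It is not shown in the documents, which give neither the limit nor the level. The BLQ rules, predose values included, show only that single BLQ values were thought possible; they do not show that all-BLQ subjects were expected.

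It is also fair that the analysis is descriptive and secondary/exploratory, with no hypothesis test, and that the subject listings in SAP 16.1 are not expressly limited to the PK set. An excluded subject would probably still be visible there.

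Three stronger readings are tempting and are not supported:
- A reader might infer that subjects without detectable exposure are removed from the very analysis of detection. The filter acts on observed total DPPC, while the objective concerns levels above endogenous. The ordinary no-rise subject is kept at zero. BLQ also means not quantifiable, which is not the same as not detectable.
- A reader might infer that all PK summaries are biased upward. That holds only if someone is dropped.
- A reader might infer a bias between arms, or that losing one of the three placebo subjects removes the placebo mean under SAP 7.1 ("If n is less than 3, only N, n, minimum, and maximum will be reported"). Under Protocol 8.5.2 placebo post-dose samples are not assayed, and Protocol Table 7 excludes placebo. There would then be no placebo post-dose mean to bias or lose.

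**Conclusion.** The concern holds in a limited form. SAP 6.3 and Protocol Table 7 select on a post-dose result and treat an all-BLQ subject differently from a quantifiable subject with no rise, although both would contribute zero to the baseline-corrected summaries. If k of 12 OP0201 subjects are all-BLQ, the factor 12/(12-k) on the means is exact, given that all 12 are otherwise evaluable and BLQ counts as zero. Whether k exceeds zero cannot be settled from the documents. The simulated sizes rest on assumed CVs and an assumed ratio of serum level to assay limit. Severity is minor and conditional.

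**What to change.** - In SAP 6.3, define the PK set as Cohort B subjects who received study drug and have at least one assayed post-dose DPPC sample, quantifiable or BLQ, without important PK deviations or events.
- Report the number and percentage of these subjects with any quantifiable post-dose value.
- State in SAP 16.2 that an all-BLQ profile has baseline-corrected Cmax of zero, and keep a quantifiable requirement only for tmax.
- Record the departure from Protocol Table 7 in SAP 4.3.
- Separately, reconcile Protocol 8.5.2 and Table 7 with SAP 6.3 on placebo. If placebo post-dose samples are not assayed, the revised definition still admits none of the three placebo subjects, so any placebo summary depends on which statement applies.

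The cost of redefining the set is wording and one added table row, with no new samples. If every subject proves quantifiable, no result changes. A geometric mean of Cmax cannot be computed with zeros, but the current plan already faces that for any no-rise subject.
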